Site coordinators will contact participants on a weekly basis by phone to assess use of the device, answer questions, and collect breathing data for the prior 7 days stored on the device.

Week 6 (mid-intervention) Data Collection

In addition to the device breathing data, the following forms will be completed by phone and/or mail. Brief questionnaires to include Self-Reported Dyspnea Anxiety/Depression/Cancer-Related Worry, Fatigue, and Cough Questionnaires.

Week 12 Data Collection

Participants will be seen in the clinic for collection of final breathing data and to complete measures: Self-Reported Dyspnea, Spirometry (FEV1), Anxiety/Depression/Cancer-Related Worry, Fatigue, Cough Questionnaires, blood draw, and salivary cortisol collection. Participants will return their RESPeRATE device to the site coordinator.

Endpoints

Feasibility (accrual, participation, adherence, retention), Anxiety, Cancer-Related Worry, Self-Reported Dyspnea, Spirometry (FEV1), Epigenetic and Gene Expression Changes, salivary cortisol changes (for those who are eligible related to Supplemental Objective 1.5)

Stratification: Site; Self-Reported Dyspnea

Study Sample: 75 participants (25 per group)

Study Duration: 12 weeks

Brief Eligibility Criteria:

- Past History of any lung cancer
- For Stage I-III disease, patients should be 2-24 months post-completion of surgery, radiation therapy and/or chemotherapy with no further planned treatment during the 12-week study and no evidence of disease.

For Stage IV disease, patients may be receiving no treatment or may be receiving maintenance treatment with a target agent, chemotherapy, or immunotherapy provided the most recent imaging does not demonstrate progressive disease.

- After completion of all three screening questionnaires, participant must score accordingly on at least one questionnaire to be eligible:
 - score ≥ 8 on the anxiety subscale of the HADS ¹ OR
 - score ≥ 4 on the Distress Thermometer ⁹²⁻⁹⁴ OR
 - score > 5 on the Modified Cancer Acceptance Scale ⁹⁶
- Eastern Cooperative Oncology Group performance status 0-2

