increase in the year after lung cancer surgery,¹⁵ and recent studies have reported rates of clinically significant anxiety among lung cancer patients and post-treatment survivors ranging from 20-30%.¹⁶⁻¹⁹

Anxiety commonly co-occurs with distressing physical symptoms in patients with lung cancer.^{18,20,21} The correlation between self-reported anxiety and dyspnea is estimated at 0.3.²¹ This relationship is bidirectional, reflecting affective and physiological processes.^{20,22-24} The number of lung cancer patients reporting dyspnea at some stage in their illness ranges from 55-90%.^{20,21,25-27} Estimates of dyspnea in post-treatment ESLC survivors range from 40-60%.^{28,29} Thus, dyspnea commonly occurs with anxiety after lung cancer treatment and is associated with worse functioning in multiple domains, greater distress, and lower quality of life.^{22,23,30-33}

Breathing interventions have been effective at reducing anxiety/distress in cancer patients. Interventions focused on slow, deep breathing have decreased anxiety, stress symptoms, and physiological arousal in clinical populations and healthy adults.³⁴⁻³⁷ Relaxation training is effective for relieving anxiety in cancer patients.^{8,10} Breathing interventions have been incorporated into interventions to address dyspnea and related distress in lung cancer patients.³⁸ Few studies have examined concomitant changes in anxiety/distress, and anxiety level has not been a criterion for study entry. Such multi-component interventions have yielded promising results for anxiety and distress related to breathlessness in post-treatment lung cancer survivors.^{39,40}

2.1b Background for Supplemental Objective: Epigenetic Changes & Anxiety

A number of recent studies have reported epigenetic changes associated with mental health and mood disorders. These have included post-traumatic stress disorder⁸¹, depression⁸², and suicide⁸³, and provide support for our hypothesis that epigenetic variation also contributes to changes in anxiety levels. Taken together, epigenetic variation in a number of individual genes and biological pathways has been identified for these conditions, and include inflammatory⁸² and immune⁸¹ related genes, as well as genes involved in the hypothalamic-pituitary-adrenal (HPA) axis.⁸⁴

2.1c Background for Supplemental Objective: Cortisol Changes & Anxiety

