6.4.2 Randomization Process

Patients will be stratified by baseline dyspnea score (Cancer Dyspnea Scale score ≥ 8 v. < 8 ; see Table 7.8) and assigned with equal probability to either RESPeRATE intervention group or the control group using variable length permuted block randomization. Block sizes will be chosen randomly to ensure that future assignments cannot be inferred from previous ones. Patients need to report a minimum level of clinically significant anxiety symptoms (HADS-Anxiety/Depression Scale anxiety subscale ≥ 8), cancer-related worry (Modified Cancer Acceptance Scale score > 5), or distress (Distress Thermometer ≥ 4) to enter the study.

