7.7 Methods for Clinical Procedures – N/A

7.8 Study Parameter Table

Consent		X				
Flow Sheet			X		X	X
Screening Form (A) (To be completed on eligible and ineligible patients that do not want to participate)		X				
HADS-Anxiety/Depression Scale ^{64-66, 68-70} (pre-screen if done by phone in advance OR at baseline if done in person).	X (C)				X	X
Distress Thermometer (1 item)	X					
Modified Cancer Acceptance Scale (2 items)	X					
Cancer Worry Scale (8 items) ⁹⁵			X		X	X
Spirometry (FEV1)			X			X
Cancer Dyspnea Scale (CDS) ^{62, 63, 67, 73} Will be needed for registration			X (D)		X	X
PROMIS Fatigue ⁷⁹			X		X	X
Manchester Cough in Lung Cancer Scale ⁸⁰			X		X	X
Activities Form			X		X	X
Current Medications			X			X
Weekly Check-In Call/Data Capture from Device (via telephone interview)			X	Weekly (1-12)		
Participant Expectations ^{74, 75}			X			
Intervention Feedback						X
Early Withdrawal Form		If patient withdraws prior to completion of study.				
RNA/DNA Labs		X				X
Salivary cortisol collection (B)		X				X
** Visual Analogue Scales for Distress, Anxiety, and Dyspnea ^{71, 72}		
Should be requested by mail and submitted at Week 6 and at completion of the Week 12 study.
 
Completed before and after a single use of the device each week during Weeks 1-12.
 
(Participant will need several double sided forms) 1 selected use/week x 12 weeks = 12 forms
				

(A) Designated staff person at each site will log-in to CCRBIS to enter data in the screening log for all potential participants screened (necessary for the Primary Study Aim examining feasibility).

- (B) *Participants with endocrine disorders (e.g., diabetes and thyroid disorders) or on steroid-based medications are excluded from the salivary cortisol portion of the study. Topical steroid medications (creams/ointments) are permitted
- (C) Pre-screen HADS may be used for baseline and does not need to be repeated.
- (D) CDS will need to be collected prior to registration

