12. STATISTICAL CONSIDERATIONS

12.1 Study Design/Endpoints

Objectives: The objectives of this pilot study are:

- 1) To evaluate the feasibility of conducting a randomized phase III study to test the efficacy of device-guided breathing in post-treatment lung cancer survivors with significant anxiety. Feasibility will be assessed using measures of accrual, participation, adherence, and retention.
- 2) To collect preliminary data on the variability and efficacy of two doses of a device-guided breathing intervention versus a usual breathing control group for reducing anxiety (primary outcome) and for improving self-reported cancer-related worry dyspnea, and respiratory functioning (secondary outcomes) in post-treatment lung cancer survivors.
- 3) To select the optimal dose of the device-guided breathing intervention (15 minutes once/day or twice/day) for a subsequent randomized study. The optimal dose will be defined as the one that results in the greatest improvement in anxiety scores at 12 weeks.

A parallel, randomized pilot study will be conducted to address these objectives. Eligible patients will be stratified initial dyspnea level and randomized with equal probability to high dose device-guided breathing, low-dose device-guided breathing, or a usual breathing control. Study endpoints include anxiety (primary outcome: anxiety subscale of the HADS-Anxiety/Depression Scale), dyspnea, and respiratory function. These constructs will be measured at baseline and 6 and 12 weeks post-randomization. Estimates of treatment efficacy will be obtained using the "intent to treat" approach. That is, all randomized patients will be included in the primary analyses whether or not they were treated according to protocol.

- 4) Supplemental Objective: To determine if changes in anxiety attributed to device-guided breathing are correlated with epigenetic (DNA methylation) and/or gene expression changes.
- 5) Supplemental Objective: To obtain preliminary data on changes in salivary cortisol (diurnal slope, cortisol awakening response, area under the curve) in each intervention group and associations between salivary cortisol and anxiety.

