12.3 Randomization and Stratification

Patients will be stratified by baseline dyspnea (0-7 versus 8+ for CDS total score) and assigned with equal probability to either RESPeRATE group or the control group using variable length permuted block randomization. Block sizes will be chosen randomly to ensure that future assignments cannot easily be inferred from previous ones. There will be no interim analyses for this pilot study, and analyses will not be done separately for each stratum.

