etc.) will be presented for each outcome measure at baseline and follow-up points stratified by treatment arm. Repeated measures (RM) ANCOVA models (fitted using PROC MIXED in SAS) will estimate the treatment effect for each outcome, test for treatment differences, and obtain adjusted post-treatment estimates of the variability of these outcomes. Estimates of outcome measure variability will be used to determine sample size for the subsequent trial. The primary RM ANCOVA model will include time, treatment arm, and the stratification factors. An unstructured covariance matrix will be used to account for the within-patient correlation over time. In secondary models, additional covariance structures (Toeplitz, Autoregressive, Compound Symmetry) will be assessed and the optimal structure will be chosen based on likelihood ratio tests for nested structures and the BIC statistic for non-nested structures. Least squares means and 95% confidence intervals will be provided for each outcome, stratified by treatment arm, and for the difference between treatment arms. Regression diagnostics and residual plots will be used to find appropriate transformations for variables in the model.

Subsequent RM ANCOVA models will include additional covariates (e.g., age, sex, stage) to correct for chance imbalances in important prognostic variables and account for variability in outcome measures due to covariates. These latter models will inform us of possible stratification factors for the subsequent trial. Limited exploratory analyses will be done to determine if the treatment effect differs for different levels of covariates (e.g., by including treatment by covariate interactions in the model) to see if the subsequent trial should be done in particular subsets of lung cancer survivors. It is likely that some data will be missing. In addition to the mixed models above, we will use multiple imputation pattern-mixture models under various assumptions (e.g., participants in the active arms who drop out would have subsequent patterns similar to participants in the control arm) to assess the sensitivity of our modeling assumptions.

The optimal dose will be defined as the one that results in the greatest improvement in anxiety scores at 12 weeks (based on estimates from the RM ANCOVA model). This dose will be used in the subsequent trial, assuming that it is one of the RESPeRATE intervention groups.

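### The primary RM ANCOVA lists only a two-level cut of baseline dyspnea, so for the CDS outcome it discards precision that the full baseline score, already collected, would give

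*Combined protocol and SAP*

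**What the plan says.** Section 12.4 describes repeated-measures ANCOVA models that "will estimate the treatment effect for each outcome, test for treatment differences, and obtain adjusted post-treatment estimates of the variability of these outcomes". The terms are listed once for all outcomes: "The primary RM ANCOVA model will include time, treatment arm, and the stratification factors". The within-patient covariance is unstructured. Later models may add further covariates, with age, sex and stage as examples.

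The dyspnea factor is a cut of the Cancer Dyspnea Scale total. Section 12.3 has "Patients will be stratified by baseline dyspnea (0-7 versus 8+ for CDS total score"), and 6.4.2 agrees: "Cancer Dyspnea Scale score ≥ 8 v. < 8". The schema reads "Stratification: Site; Self-Reported Dyspnea", whereas 6.4.2 and 12.3 do not name site, so which factors enter the model is itself unclear.

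The full score exists for everyone randomized. Note D to the table in 7.8 says "CDS will need to be collected prior to registration". The CDS is repeated at Weeks 6 and 12, and dyspnea is a clinical endpoint. On timing, 12.1 says of the endpoints: "These constructs will be measured at baseline and 6 and 12 weeks post-randomization". It does not say whether baseline is a response or a covariate.

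Section 12.5, by contrast, names the baseline level as a covariate for the cortisol, methylation and expression models.

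**The concern.** For the CDS outcome, a patient's baseline score is normally among the best available predictors of the follow-up score. A two-level cut keeps only part of that prediction. A baseline of 8 is treated like any higher score, and a baseline of 0 like a 7, and the differences within each level stay in the error term.

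This pilot is meant to deliver effect estimates with intervals and adjusted estimates of variability for sizing the next trial. With about 20 evaluable patients per arm, a needlessly large residual variance widens the dyspnea intervals. It would also carry into later planning if dyspnea were used there.

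**Working it through.** **The plan's own figures.** Section 12.2 assumes means of 0, -0.5 and -1.0 SD with SD 1 and 20 per group. The SD of a difference in means is sqrt(2/20) = 0.316, and each required margin is 0.5/0.316 = 1.58. The probability of selecting the high-dose arm with its mean at least 0.5 SD below control is the probability that two standard normals with correlation 0.5 both fall below 1.58, which is 0.901. The probability of stopping under no effect has the same form, also 0.901. Accrual is 60/0.8 = 75. All three figures reproduce. They use unadjusted anxiety means, so the point below does not affect them.

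**Inputs for the loss**
- r, the baseline-to-follow-up CDS correlation: not in the documents; assumed 0.5, 0.6 or 0.7.
- q, the share at or above 8: not in the documents; assumed 30% to 70%.
- A normal score and a linear relation: assumed.
- For anxiety, section 2.1a: "The correlation between self-reported anxiety and dyspnea is estimated at 0.3". This is used as a stand-in for the correlation of baseline CDS with follow-up HADS anxiety, which the documents do not report.

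**Share kept by the cut.** The squared correlation of a normal score with its cut version is k² = φ(z)²/[q(1-q)]. At q = 50%, k² = 0.637; at q = 30% or 70%, k² = 0.576.

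**Residual variance, cut relative to continuous score**
- Follow-up score modelled: (1 - r²k²)/(1 - r²).
- Change from baseline modelled: [(1 - r²) + (1 - r)²(1 - k²)]/(1 - r²).

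| r | follow-up, q = 50% | follow-up, q = 30% or 70% | change, q = 50% | change, q = 30% or 70% |
|---|---|---|---|---|
| 0.5 | 1.121 | 1.141 | 1.121 | 1.141 |
| 0.6 | 1.204 | 1.239 | 1.091 | 1.106 |
| 0.7 | 1.349 | 1.408 | 1.064 | 1.075 |

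Example (r = 0.7, q = 50%, follow-up): (1 - 0.49 × 0.637)/0.51 = 0.688/0.51 = 1.349.

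**Interval width** (square root of the ratio). Follow-up: sqrt(1.121) = 1.06 to sqrt(1.408) = 1.19. Change: sqrt(1.064) = 1.03 to sqrt(1.141) = 1.07.

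**Information lost among 60 completers, follow-up modelled.** 60 × (1 - 1/1.1211) = 6.48 and 60 × (1 - 1/1.408) = 17.4, so about 6 to 17 patients.

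**HADS anxiety at r = 0.3.** (1 - 0.09 × 0.637)/0.91 = 1.036 and (1 - 0.09 × 0.576)/0.91 = 1.042: about 4% in variance and 2% in interval width.

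**Finite-sample check.** The SD of an arm difference was simulated with 20 per arm, three arms, a median split and 4,000 repetitions:

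| r | cut only | continuous only | both |
|---|---|---|---|
| 0.5 | 0.297 | 0.279 | 0.282 |
| 0.7 | 0.260 | 0.226 | 0.227 |

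Keeping the cut beside the continuous score costs almost nothing.

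**Sensitivity to shape.** For right-skewed (gamma, shape 1 or 2) scores, k² is 0.62 to 0.64 when 30% lie at or above the cut, but 0.30 to 0.39 when 70% do. The range above is therefore not an upper limit.

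**The case against.** Five points can be made for the plan.

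- **ANCOVA may already imply the baseline value as a covariate.** That is possible, but 12.4 does not say so, and 12.5 does where it is wanted. If it is meant, one sentence settles it.
- **Baseline may be a response row under the unstructured covariance.** The listed terms would still not recover the loss. A single arm effect over three times averages in the pre-treatment difference: under compound symmetry each time has weight 1/3, so a constant post-baseline effect shrinks to 2/3. A free arm-by-time term, which is not listed, would give a Week 12 contrast unadjusted for the baseline score. A model constraining the arms to a common baseline would recover the precision, but none is described.
- **The size depends on what is modelled.** This stands. Section 12.8 defines response as change in anxiety, and 12.4 selects the dose on improvement. If that carries over to dyspnea, the loss is 6-14% and shrinks as r rises.
- **The consequences are limited.** This also stands. Dyspnea is secondary in a pilot whose primary objective is feasibility, no precision target is set for it, and an inflated residual SD would err towards a larger next trial.
- **Later models are open to more covariates.** This is true, but it does not reach the primary model.

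The gap is also wider than dyspnea: 12.4 does not say how any outcome's own baseline enters, including HADS anxiety. The fix should cover them all.

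**Conclusion.** The point holds as a matter of efficiency. As 12.4 is written, the CDS analysis uses only a two-level form of its own baseline. Under the stated assumptions for r, q and shape, residual variance is about 12-41% larger than necessary if follow-up scores are modelled (intervals 6-19% wider, about 6 to 17 of 60 completers' information). It is about 6-14% larger if change is modelled (intervals 3-7% wider). For HADS anxiety the cut costs about 4% of variance.

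A reader might infer more than this, in three ways that the documents do not support:
- **That the treatment comparison is biased or invalid.** Allocation is randomized and the stratification factor is in the model, so the comparison stays valid.
- **That the sample size or dose choice is undermined.** N = 75 rests on unadjusted anxiety means. Dose selection and the go/no-go rule use anxiety alone, where the cut costs about 4%. What is lost by leaving out baseline HADS anxiety itself is a separate matter; the documents give no correlation for it, and it is not sized here.
- **That the top of the range is an established loss.** It needs r = 0.7, an uneven split and follow-up scores modelled without their own baseline. It should be counted against the 60 planned completers, not all 75 patients.

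**What to change.** In 12.4, state that:
- the Week 6 and Week 12 values are the responses (Week 12 only for FEV1, which 7.8 does not schedule at Week 6);
- the continuous baseline value of the outcome being analysed enters the primary model as a covariate: CDS total for dyspnea, HADS anxiety for anxiety, and likewise for cancer worry and FEV1;
- the dyspnea stratification factor stays in the model, and the stratification factors are named, resolving whether site is one of them.

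Baseline must not be both a covariate and a response row. With a common slope and an unstructured covariance, a slope of 1 would make the baseline residual exactly zero and the fit would degenerate. With the continuous baseline as covariate, analysing follow-up or change gives the same treatment effect and residual variance, so that ambiguity also disappears.

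The cost is a few lines of text and no new data. The small downside is a linearity assumption, which the residual plots already planned in 12.4 would check.

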12.2 Sample Size/Accrual Rate

The sample size for this trial will be based on statistical selection theory criterion as described by Simon et al.⁷⁷ For a selection trial, one simply chooses the regimen that results in the "best" response. While Simon used this idea in the context of choosing the regimen with the best tumor response, the idea is applicable to outcomes with other distributions (in addition to the binomial). In our trial, the response is self-reported anxiety, which we will assume is normally distributed, so the best regimen will be the one with the lowest mean anxiety score. We will proceed to a phase III trial if one of the RESPeRATE intervention arms results in the least anxiety, and the mean anxiety score in that group is at least 0.5 standard deviations (SD) less than mean anxiety score in the control group. The sample size is chosen to ensure a high probability of selecting the best arm, assuming that the mean anxiety score in the low dose arm is 0.5 SD less than the mean in the control group and the mean anxiety score in the high dose arm is 1.0 SD less than the mean in the control arm. Under these assumptions, we used

simulations to determine the sample size needed in each group to ensure that the probability of selecting the best regimen was 90%. We randomly selected n independent observations from the normal distribution with an SD = 1, calculated the mean anxiety scores for each group, and selected the group with the least observed mean. This was repeated 200,000 times. The probability that the best regimen was chosen is calculated as the proportion of times (of the 200,000 repetitions) that the group with the true lowest mean was selected. In addition to selecting the best regimen, we will only pursue a subsequent phase III trial if there is some evidence of effect. Thus, we will require that the mean in the best regimen is at least 0.5 SD lower than the mean for the control group. Using simulations, we find that 20 patients per group provides 90% probability that the best regimen will be chosen and the mean in that group be at least 0.5 SD lower than the mean in the control arm. Assuming a 20% dropout, we will accrue a total of 75 participants to this study (20x3/.8). Assuming no effect of the RESPeRATE device, we have 90% probability of stopping with the phase II trial.

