12.4 Primary Endpoint(s)

The primary objective of this study is to collect data that will allow us to assess the feasibility of conducting a phase III randomized study of device-guided breathing in lung cancer survivors with significant anxiety. These endpoints include: participation, accrual, adherence, and retention.

The participation rate will be calculated as the proportion of eligible patients who agree to participate.

The accrual rate will be calculated as the number of patients accrued to the study divided by the number of months of accrual.

The actual amount of time the participant used the device will be retrieved from each device. Adherence will be calculated as the actual amount of time the device is used divided by the prescribed time. Successful adherence will be defined as use of the device $\geq 75\%$ of the time assigned. We will also estimate the proportion of patients who use the device more than prescribed. (If “low-dose” participants use the device more than prescribed, this may limit our ability to detect a dose effect.)

Retention will be calculated as the number of participants who complete the final assessment divided by number randomized.

Confidence intervals for the binomial proportions will be calculated using methods described by Wilson.⁷⁸ Approximate 95% confidence intervals based on the normal distribution will be calculated for the continuous measures.

The clinical endpoints are anxiety (primary outcome: anxiety subscale of the HADS-Anxiety/Depression Scale), cancer-related worry, dyspnea, and pulmonary function at baseline and 6 and 12 weeks post-randomization. Estimates of treatment efficacy will be obtained using the “intent to treat” approach. Descriptive statistics (means, standard deviations, frequencies,

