Assuming the 95% confidence interval for the treatment effect includes a clinically meaningful difference, the sample size for the subsequent phase III trial will be determined based on detecting a clinically meaningful difference with a high power using estimates of variability obtained in this study. The estimates of retention and adherence observed in this study will be used to refine that sample size estimate. Subsequent trial feasibility will be assessed based on our ability to recruit the required number of participants. For that, we will use the accrual and participation rates observed in the participating sites. For sites that did not participate in this pilot study, accrual will be estimated by multiplying the estimated number of eligible patients times the participation rate across the participating sites.

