Salivary Cortisol Analyses. Participants with endocrine disorders (e.g., diabetes and thyroid disorders) or on steroid-based medications are excluded from the cortisol portion of the study (topical hydrocortisone cream permitted). Cortisol levels will be assessed upon awakening, 30 minutes post-awakening, and at bedtime for three consecutive days at baseline and three consecutive days at 12 weeks. Several measures will be derived from the three daily cortisol values, including the mean levels at each time, the mean cortisol awakening response (CAR – change in cortisol from awakening to 30 minutes), the area under the curve (AUC), and the diurnal slope (change in cortisol between awakening and bedtime). Scatterplots and correlations will be used to quantitate the associations between these measures, and anxiety at each time (baseline and 12 weeks) as well as association between the change in cortisol measures and the change in anxiety. Additionally, mixed effects models, as described above, will be used to assess the association between baseline cortisol and changes in anxiety over time. To assess group differences in cortisol parameters, each of these measures at 12 weeks will be used as dependent variables in analysis of covariance models, using appropriate transformations as needed. Baseline levels of the measures will be used as covariates along with treatment group.

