12.8 Evaluation of Response

Tumor response is not an outcome. Response for this study will be the change in anxiety from baseline to 12 weeks, and this outcome will be assessed in all participants. Analysis of this outcome is described above in Section 12.4.

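### Section 12.4 picks the dose on the 12-week anxiety effect, but the primary model as listed has no arm-by-time term and so yields one arm difference averaged over visits

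*Combined protocol and SAP*

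**What the plan says.** Section 12.4 specifies the primary clinical analysis: "The primary RM ANCOVA model will include time, treatment arm, and the stratification factors". The covariance is unstructured. Least squares means are promised by arm and for arm differences, with no mention of visit.

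The same section defines the optimal dose by the "greatest improvement in anxiety scores at 12 weeks (based on estimates from the RM ANCOVA model"). The third objective in Section 12.1 sets the same 12-week target. Section 12.8 states "Response for this study will be the change in anxiety from baseline to 12 weeks" and refers the analysis back to 12.4. No section adds an arm-by-time term or a separate week-12 contrast for anxiety.

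How baseline anxiety enters is not stated. Section 12.4 lists the clinical endpoints, anxiety first, ending with "pulmonary function at baseline and 6 and 12 weeks post-randomization". It then speaks of adjusted post-treatment estimates, but baseline is not among the model terms. For cortisol, by contrast, Section 12.5 is explicit: "Baseline levels of the measures will be used as covariates along with treatment group".

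Two further decisions name no visit. Section 12.2 goes on to phase III only if an active arm ranks best and also meets this condition: "the mean anxiety score in that group is at least 0.5 standard deviations (SD) less than mean anxiety score in the control group". Section 12.4 makes phase III sizing conditional: "Assuming the 95% confidence interval for the treatment effect includes a clinically meaningful difference".

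**The concern.** A model with time and arm as main effects fits one arm difference for all modelled visits. Week-12 least squares means can be printed from it, but their differences are that same common difference. It is a weighted average of the visit-specific effects, with weights set by the visit variances and correlations, so week 12 need not dominate.

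The direction of error depends on what the plan leaves open:

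- **Diluted** if onset is gradual, or if baseline is one of the repeated outcomes.
- **Unbiased** if only weeks 6 and 12 are outcomes and the effect is complete by week 6.
- **Inflated** if the week-6 effect is the larger one.

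If the two doses differ in speed of onset, their ranking can tie or reverse even though the 12-week ranking is clear. Choosing the dose is a stated objective, and the chosen dose goes into the next trial.

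**Working it through.** **Inputs from Section 12.2:** 20 evaluable per arm; SD 1; low dose 0.5 SD and high dose 1.0 SD below control; go threshold 0.5 SD. **Assumptions (the documents give none of these):** the effects are week-12 effects; visit correlation ρ is 0.5 to 0.8; visit variances are equal unless stated; the 0.5 SD rule is applied to the model's estimate.

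**1. The plan's own figures, one observation per patient.** SE of an arm difference = √(2/20) = 0.316.
- Low ranked ahead of high: Φ(−0.5/0.316) = 5.7%.
- High dose lowest and at least 0.5 SD below control: control − high has mean 1.0, low − high has mean 0.5, both have variance 0.10 and their covariance is 0.05. P(first ≥ 0.5 and second ≥ 0) = 0.901, against 90% stated.
- Stopping under no effect, by simulation: 0.901, against 90% stated.
- Total: 60/0.8 = 75, as stated.

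**2. What the listed model estimates.** With S the covariance matrix of the modelled visits, the weights are w = S⁻¹1/(1′S⁻¹1) and the per-patient variance is v = 1/(1′S⁻¹1). For weeks 6 and 12 with equal variances, w = (0.5, 0.5) and v = (1+ρ)/2 = 0.75 to 0.90. The SE is √(2v/20) = 0.274 to 0.300.

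**3. Weeks 6 and 12 as outcomes.** Under linear onset the high-dose effect is 0.5×0.5 + 0.5×1.0 = 0.75 and the low-dose effect is 0.5×0.25 + 0.5×0.5 = 0.375. The gap is 0.375. Wrong ranking is Φ(−0.375/0.274) = 8.5% to Φ(−0.375/0.300) = 10.6%. The same steps give:

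| Week-6 effect relative to week 12 | High selected and go | Low ranked ahead of high |
|---|---|---|
| Single time point (step 1) | 0.90 | 5.7% |
| Half (linear) | 0.75–0.78 | 8.5–10.6% |
| 75% | 0.85–0.88 | 5.5–7.2% |
| Equal (full by week 6) | 0.92–0.94 | 3.4–4.8% |
| 25% larger | 0.96–0.97 | 2.0–3.0% |
| Low dose full, high dose half | 0.68–0.71 | 18–20% |
| Low dose full, high dose none | 1/3 | 50% |

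In the last row both doses average 0.5 SD, so they tie, and the joint probability is 1/4 + arcsin(0.5)/(2π) = 1/3. Ranking can also reverse. Suppose the low dose gives 1.0 SD at week 6 and 0.5 at week 12, and the high dose 0.4 and 1.0. The averages are 0.75 and 0.70, and at ρ 0.5 to 0.7 the listed model ranks the high dose first 43% of the time, against 94% for the week-12 contrast. Stopping under no effect rises to 0.92–0.94.

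**4. Unequal variances.** With week-6 SD 0.8 of week-12 SD, the week-6 weight is (1 − 0.8ρ)/(1.64 − 1.6ρ): 0.60/0.84 = 71% at ρ = 0.5 and 0.36/0.36 = 100% at ρ = 0.8.

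**5. Baseline also an outcome.** Under compound symmetry the weights are one third each, so a 1.0 SD week-12 effect is estimated as 0.50 (linear) or 0.67 (full by week 6). Selection with go, over compound symmetry and AR(1), is 0.46–0.47 or 0.52–0.70.

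**6. Baseline as covariate, linear onset.** Selection with go is 0.84–0.93 under compound symmetry and 0.68–0.76 under AR(1). The baseline-adjusted week-12 contrast gives 0.91–0.99.

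**7. Check with estimated unstructured covariance** (20,000 simulated trials per cell, weeks 6 and 12, ρ = 0.5 / 0.8):
- Linear: 0.769 / 0.732.
- 75% at week 6: 0.878 / 0.845.
- Full by week 6: 0.938 / 0.914.
- Low full, high linear: 0.709 / 0.670, wrong ranking 18.7% / 21.8%.
- Linear with week-6 SD 0.8: 0.684 / 0.470.
- Week-12 means on the same linear-onset data (equal variances): 0.901 / 0.900.

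Estimating the covariance makes the listed model slightly worse than the formulas at ρ = 0.8.

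**The case against.** The fairest reply is that this is an omission in a prose summary. The text does not say that only these terms are included; a 12-week estimate from the model implies that week-specific estimates were expected; and a model called ANCOVA that leaves baseline off its list suggests the list is incomplete. That may be so, but nothing in the documents says it. The plan does name interactions when it wants them ("by including treatment by covariate interactions in the model", though for exploratory subgroup work). An analyst following the list would fit main effects.

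Other points stand in part:

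- **Ranking versus go.** Most of the larger losses come from combining selection with the 0.5 SD rule, which Section 12.2 never ties to this model. On ranking alone, with weeks 6 and 12 as outcomes and doses sharing an onset shape, the error reaches only 8.5–10.6% under linear onset and improves to 3.4–4.8% if the effect is full by week 6. Serious ranking harm there needs doses with different onset, which no section predicts or rules out.
- **Baseline adjustment.** With baseline as covariate, wrong ranking under linear onset is 1.0–4.7% (compound symmetry) or 5.5–7.7% (AR(1)), near or below the 5.7% reference. This widens the range of outcomes, but the adjusted week-12 contrast still does better.
- **Pilot context.** Feasibility is the primary objective, and arm means at each follow-up will be reported, so a discrepancy would be visible. The dose rule, however, takes the model's estimate.

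**Conclusion.** The concern holds and should be fixed. That the listed terms cannot give a distinct 12-week arm contrast is certain from the text. The consequence is conditional on week-6 effects, visit correlations, variances and the handling of baseline, none of which the documents give.

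Under linear onset, with the 0.5 SD rule applied to the model's estimate, the 90% in Section 12.2 becomes roughly 0.73–0.78 with weeks 6 and 12 as outcomes and equal variances. It becomes 0.68–0.93 with baseline as covariate and 0.46–0.47 with baseline as a third outcome. If the effect is constant over weeks 6 and 12 and only those are outcomes, nothing is lost. The Section 12.2 calculation is itself sound for one score per patient; it simply does not carry over to the listed model.

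**What to change.** In Section 12.4:

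1. Add arm-by-time to the primary model, with time as a categorical factor.
2. State how baseline HADS anxiety enters: either as a covariate with weeks 6 and 12 as outcomes, or as an outcome with the arms constrained equal at baseline.
3. State that the week-12 contrasts (each dose against control, and high against low) are the estimates used for dose selection, for the 0.5 SD rule in Section 12.2, and for the confidence-interval condition on phase III sizing.

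This needs no new data, visits or participants. Some precision is given up if the effect really is constant: without baseline adjustment the week-12 SE is 0.316 SD, against 0.274–0.300 for the two-visit average. But 0.316 is what the 90% in Section 12.2 already assumes. With baseline as covariate, the week-12 variance is 0.36 to 0.94 under the assumed correlations, so the SE is √(2×0.36/20) = 0.19 to √(2×0.94/20) = 0.31.
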